Data from the 2 studies with respect to ocrelizumab group versus Rebif group will be pooled for analysis of this endpoint.

The proportions in treatment groups will be compared with use of the Cochran-Mantel-Haenszel (CMH) χ^2 test stratified by geographical region (United States vs. ROW) and baseline EDSS score (< 4.0 vs. ≥ 4.0).

8.2.2.5 The Time to Onset of Confirmed Disability Progression for At Least 24 Weeks During the 96-Week Comparative Treatment Period

Time to confirmed disability progression between ocrelizumab group and Rebif group with use of a 24-week confirmation window for disability progression will be compared with use of the same analysis method for time to confirmed disability progression using a 12-week confirmation window. Time to confirmed disability progression (24-week confirmation) is defined as the time from baseline (Day 1) to the first disability progression, which is confirmed at the next regularly scheduled visit ≥ 161 days after the initial disability progression. All initial disability progression events up to Week 96 with corresponding confirmation visits at the next schedule visit (see schedule of activities in Section 1.3) will be taken into account for the statistical analysis. The same analysis

principles as described in Section 8.2.2.1 will be applied to the 24-week disability endpoint.

Data from the 2 studies with respect to ocrelizumab group vs. Rebif group will be pooled for analysis of this endpoint.

8.2.2.6 Total Number of New T1-Hypo-Intense Lesions (Chronic Black Holes) at Weeks 24, 48, and 96

The same approach will be used for the statistical analysis as for the total number of T1 Gd-enhanced lesions.

8.2.2.7 The Change in MSFCS Score from Baseline to Week 96

The change in MSFCS from baseline to Week 96 will be compared between ocrelizumab group and Rebif group with use of a Mixed-Effect Model Repeated Measures (MMRM) analysis, adjusting for baseline MSFCS, region (United States vs. ROW), and baseline EDSS (<4.0 vs. ≥4.0).

8.2.2.8 The Percentage Change in Brain Volume as Detected by Brain Magnetic Resonance Imaging Scan from Week 24 to Week 96

The change in brain volume as detected by brain MRI from week 24 to Week 96 will be compared between ocrelizumab group and Rebif group with use of an MMRM analysis. Baseline covariates here will be as follows: brain volume at Week 24, baseline Gd lesion (present or not), region (United States vs. ROW), and baseline EDSS score (<4.0 vs. ≥4.0).

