- The fifth secondary efficacy endpoint is the time to onset of confirmed disability progression for at least 24 weeks, with the initial event of neurological worsening occurring during the 96-week, double-blind, double-dummy treatment period, but the modality being tested here (EDSS) is identical to that of the first secondary endpoint. Given that the number of 24-week CDP events will be lower than the number of 12 week CDP events, there is likely a lower chance of achieving a statistically significant treatment difference, and hence, the 24 week CDP is listed lower than the 12 week CDP. It is, however, listed relatively higher in the hierarchy as the fifth endpoint, given the greater clinical meaningfulness of disability progression than the remaining endpoints.
- The sixth and eighth secondary endpoints, chronic black holes and brain volume, are indicators of brain tissue loss. The possible correlation of such brain-atrophy measures and long-term clinical outcomes has been suggested in other studies ([Barkhof et al. 2009](#)). Therefore, because they are imaging modalities and the correlation to clinical outcomes is weaker than the imaging endpoints that are listed higher in the hierarchy, these endpoints are listed lower in the hierarchy than the clinical endpoints.
- The EDSS does not adequately assess upper limb function and cognitive impairment; therefore, the MSFC scale is used to address this gap in clinical disability assessment. However, since the MSFC scale is not as widely used in other studies and not as well-accepted as a validated endpoint, it is listed seventh in the hierarchy.
- The SF-36 is one of the most widely used and validated instruments for measuring quality of life in patients with MS. It is, however, listed as ninth in the hierarchy below all the other clinical measures because quality-of-life instruments in general are not as widely used in confirmatory clinical studies compared with the other clinical measures.

- The tenth and final secondary endpoint is a composite measure encompassing the absence of disease activity based on clinical and MRI parameters (i.e., consisting of the primary endpoint and secondary endpoints 1, 2, and 3 above). It is a highly meaningful endpoint for patients but is listed as last in the hierarchy because it is a combination of previous secondary endpoints.

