- The seventh (and subsequent) secondary efficacy endpoint will be tested in a confirmatory manner if and only if the sixth (or immediately previous) secondary efficacy endpoint reaches a significance level of 0.05 (i.e., $p \leq 0.05$). If the sixth (or immediately previous) secondary efficacy endpoint $p > 0.05$, then the seventh (or current) and all subsequent secondary efficacy endpoint p-values within the hierarchy will be interpreted as non-confirmatory.

Furthermore, for analyses of secondary efficacy endpoints where data from both studies are combined (so there is sufficient statistical power for all primary and secondary efficacy endpoint comparisons):

[figure not shown]
- The first secondary efficacy endpoint (the time to onset of confirmed disability progression for at least 12 weeks) will be tested in a confirmatory manner if and only if the primary efficacy endpoint (annualized protocol-defined relapse rate by 2 years), reaches a significance level of 0.05 (i.e., pooled analysis $p \leq 0.05$). If the primary efficacy endpoint pooled analysis $p > 0.05$, then all secondary efficacy endpoint pooled analysis p-values within the hierarchy will be interpreted as non-confirmatory.
- The second (and subsequent) secondary efficacy endpoint will be tested in a confirmatory manner if and only if the first (or immediately previous) secondary efficacy endpoint reaches a significance level of 0.05 (i.e., pooled analysis $p \leq 0.05$). If the first (or immediately previous) secondary efficacy endpoint pooled analysis $p > 0.05$, then the second (or current) and all subsequent secondary efficacy endpoint pooled analysis p-values within the hierarchy will be interpreted as non-confirmatory.

The sequence of the confirmatory testing is illustrated in [Figure 1](#) below.

The arrows on the left illustrate the hierarchy of the statistical tests of Study WA21092. The arrows on the right illustrate the hierarchy of the statistical tests of Study WA21093. The boxes in the middle highlight the analyses performed in the pooled data set of WA21092 and WA21093.

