4.4.2.3.1 OLE Phase

CDP12 analysis cannot be repeated for the OLE phase since EDSS assessments are performed only at every 24 weeks post OLE Week 24.

4.4.2.4 Total Number of T1 Gadolinium–Enhanced Lesions as Detected by Brain Magnetic Resonance Imaging at Weeks 24, 48, and 96

The total number of T1 Gd–enhanced lesions will be calculated as the sum of the individual number of T1 Gd–enhanced lesions at Weeks 24, 48, and 96. Data from other unscheduled assessments will not be included in this summary or analysis.

The same approach to analysis will be applied here as described in Section 4.4.1, “Analysis Methods” section, with the following exceptions:

- In order to account for patients receiving varying numbers of brain MRI scans during the study, the log-transformed number of brain MRI scans received will be included in the model as an “offset” variable for appropriate computation. This approach is preferable to imputation of missing values using the average of non-missing

observations, because only three timepoints would give a high variability in the imputed average values. Additionally, the “offset” variable approach aligns more closely with approaches to analysis used a) in regulatory submissions for other MS therapies, b) for the primary endpoint, and c) in this program’s Phase II study.

- Baseline covariates here will be as follows: baseline Gd lesion (present or not), treatment group, baseline EDSS score (<4.0 vs. ≥4.0), and geographical region (United States vs. ROW).

Sample SAS code can be found below (SAS code is regarded as “draft” until fully validated at the analysis stage):

```
proc genmod data=MRIT1;
  class ARMCD REGION BEDSSCAT BGDLESFL;
  model N MRIT1 = ARMCD REGION BEDSSCAT BGDLESFL /
  offset=MRILOG link=log dist=negbin type3;
  lsmeans ARMCD / exp cl;
  ods output lsmeans=ls;
  ods output ParameterEstimates=est;
run;
```

If the model fails to converge due to high number of zero T1 lesion counts, a logistic regression model will be performed on Gd lesion (present or not) adjusted for the same baseline variables. Patients withdrawn from treatment and having no T1 lesions: those withdrawn because of lack of efficacy or death are considered as having T1 lesions; otherwise, it will be considered a missing observation:

```
proc logistic data=MRIT1;
  class ARMCD REGION BEDSSCAT BGDLESFL;
  model N MRIT1 CAT = ARMCD REGION BEDSSCAT BGDLESFL;
  oddsratio ARMCD /cl=wald;
  ods output OddsRatiosWald = oddsr;
run;
```

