The model will be implemented in SAS using the MIXED procedure and will include the change from baseline in MSFC score as the dependent variable. The fixed effects in the model will include independent variables of randomized treatment, visit (nominal post \leq baseline visits as per the Schedule of Assessments) and treatment-by-visit interaction, along with the following baseline covariates: baseline MSFC score, baseline MSFC score by visit interaction, geographical region (United States vs. ROW), and baseline EDSS score (<4.0 vs ≥ 4.0). Visit will be treated as a repeated variable within a patient. Patient, treatment, and visit will be treated as factor variables. An unstructured variance–covariance structure will be applied to model the within-patient errors. The model will be fitted using the Restricted Maximum Likelihood method (REML). Denominator degrees of freedom will be estimated using Satterthwaite’s approximation.

To estimate the difference between the ocrelizumab and interferon beta-1a 44 μ g SC groups in mean change from baseline to Week 96, a treatment-by-visit interaction contrast will be constructed (i.e., the treatment group contrast at Week 96). On the basis of this analysis, least square means, standard errors, and the 95% confidence interval for the treatment difference will be reported.

Graphical presentations for least square means and 95% confidence intervals will be used to illustrate trends over time.

Sample SAS code can be found below (SAS code is regarded as “draft” until fully validated at the analysis stage):

```
proc mixed data=MSFCS method=REML;
  class REGION BEDSSCAT ARMCD VISIT USUBJID;
  model change = BFCS REGION BEDSSCAT ARMCD VISIT
```

```

BFCS*VISIT ARMCD*VISIT / ddfm= satterthwaite;
repeated VISIT / type=un subject = USUBJID;
lsmeans ARMCD*VISIT / pdiff cl;
ods output lsmeans = lsm; * contains the adjusted means;
ods output diffs = dif; * contains treatment differences;
run;

```

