4.4.2.9.1 OLE Phase

This analysis won't be repeated for the OLE phase as this data is not being collected during the OLE phase.

4.4.2.10 Percentage Change in Brain Volume as Detected by Brain Magnetic Resonance Imaging Scan from Week 24 to Week 96

Brain volume is recorded as an absolute “normalized” value at the baseline visit then recorded at subsequent visits as a percentage change relative to the absolute value at the baseline visit. Therefore, brain volume at Week 24 will be calculated as the brain volume at the baseline visit multiplied by $1 + ([\text{percentage change in brain volume from baseline visit to Week 24}]/100)$. This value will be used to determine the percentage change in brain volume at Weeks 48 and 96 relative to Week 24.

Percentage change in brain volume relative to Week 24, as detected by brain MRI scan, will be computed and summarized at Weeks 48 and 96 using descriptive statistics for each treatment group. Data from other unscheduled assessments will not be included in this summary or analysis.

For the assessment of differences in the mean percentage change in brain volume on MRI scans from Week 24 to Week 96, an MMRM analysis will be undertaken using the same approach as described in Section 4.4.2.9, except for the following:

- The response variable will be the percentage change from Week 24 to subsequent visits (Weeks 48 and 96). Baseline brain volume data will not feature in this analysis.
- Baseline covariates here will be as follows: brain volume at Week 24, geographical region (United States vs. ROW), and baseline EDSS score (<4.0 vs ≥ 4.0)
- To estimate the difference between the ocrelizumab and interferon beta-1a 44 µg SC groups in mean change from Week 24 to Week 96, a treatment-by-visit interaction contrast will be constructed (i.e., the treatment group contrast at Week 96)

Sample SAS code can be found below (SAS code is regarded as “draft” until fully validated at the analysis stage):

```

proc mixed data=MRINBV method=REML;
class REGION BEDSSCAT ARMCD VISIT USUBJID;
model change = W24NBV REGION BEDSSCAT ARMCD VISIT
W24NBV*VISIT ARMCD*VISIT / ddfm= satterthwaite;
repeated VISIT / type=un subject = USUBJID;
lsmeans ARMCD*VISIT / pdiff cl;
ods output lsmeans = lsm; * contains the adjusted means;
ods output diffs = dif; * contains treatment differences;
run;

```

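### The SAP's brain-volume model omits, without explanation, the baseline Gd-lesion covariate that the protocol specifies

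*SAP*

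**What the plan says.** Protocol 8.2.2.8 specifies an MMRM for this endpoint with these covariates: "brain volume at Week 24, baseline Gd lesion (present or not), region (United States vs. ROW), and baseline EDSS score" (in two categories, split at 4.0).

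SAP 4.4.2.10 covers the same endpoint with the same type of model, but gives a shorter list: "Baseline covariates here will be as follows: brain volume at Week 24, geographical region (United States vs. ROW), and baseline EDSS score", with the same split. The sample code follows the shorter list. Its class statement is "class REGION BEDSSCAT ARMCD VISIT USUBJID". Its model statement begins "model change = W24NBV REGION BEDSSCAT ARMCD VISIT" and continues only with the interactions of visit with Week 24 volume and with treatment.

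On the endpoint's standing, SAP 4.4.2.1 says "The sixth and eighth secondary endpoints, chronic black holes and brain volume, are indicators of brain tissue loss". SAP 4.4.2.2 adds "The seventh (and subsequent) secondary efficacy endpoint will be tested in a confirmatory manner if and only if the sixth" endpoint, or whichever comes immediately before, is significant at 0.05. The order after chronic black holes is MSFC, brain volume, SF-36 PCS, NEDA.

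**The concern.** Two current documents give different models for one endpoint in a fixed-sequence hierarchy. If testing reaches the eighth step, the p-value from that step decides whether SF-36 PCS and NEDA can be tested confirmatorily. A reader should be able to tell from the plan which model supplies that p-value. Here the longer covariate list is in the protocol, the shorter one is in the SAP, and nothing says that the difference is intended. There is also a minor statistical cost: a baseline covariate that the protocol considered worth adjusting for is left out.

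**Working it through.** **Is the omission real, or does the term enter another way?**

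| Place | Covariates besides treatment and visit | Gd term? |
|---|---|---|
| Protocol 8.2.2.8 | Week 24 volume, baseline Gd lesion, region, EDSS category | Yes |
| SAP 4.4.2.10, text | Week 24 volume, region, EDSS category | No |
| SAP 4.4.2.10, code | `W24NBV`, `REGION`, `BEDSSCAT`, `W24NBV*VISIT` | No |
| SAP 4.4.2.9, whose approach 4.4.2.10 adopts | "baseline MSFC score, baseline MSFC score by visit interaction, geographical region (United States vs. ROW), and baseline EDSS score" | No |

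Text and code agree with each other, so this is not a slip in one of them, and the cross-reference to the MSFC section does not bring the term in.

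**Is it explained?** The amendment rationale at the front of the SAP claims alignment with the amended protocols. The May 2015 list of updates and the January 2022 list of analyses modified after unblinding do not mention this covariate. Where the SAP recognised a difference from the protocol, it could say so: SAP 4.4.2.8 notes that the protocol had not made clear that only new T1-hypointense lesions count. There is no such note for brain volume. For the other two secondary MMRM endpoints, MSFC and SF-36 PCS, the protocol and SAP name the same baseline covariates, apart from the SAP's added baseline-by-visit interaction.

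**Is the variable available?** Yes. SAP 4.4.2.4 uses it for the Gd-lesion count, "Baseline covariates here will be as follows: baseline Gd lesion (present or not), treatment group" and so on, coded as `BGDLESFL`. SAP 4.4.1 and 4.4.2.3 add baseline Gd status in sensitivity analyses of relapse rate and disability progression.

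**How much could it matter?** No figure in the plan depends on this covariate, so there is none to reproduce. The documents give no R² for baseline Gd status on brain-volume change. As an illustration, assume R² between 0.01 and 0.10 of residual variance, balanced arms and an unchanged estimate:

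- SE ratio (with / without) = √(1 − R²)
- Equivalent gain in patients = 1/(1 − R²) − 1
- A p of 0.050 without the term becomes 2[1 − Φ(1.96 / ratio)]
- Largest p without the term that reaches 0.05 with it = 2[1 − Φ(1.96 × ratio)]

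| R² | SE ratio | Gain in patients | p = 0.050 becomes | p that falls to 0.05 |
|---|---|---|---|---|
| 0.01 | 0.995 | 1.0% | 0.0489 | 0.0512 |
| 0.02 | 0.990 | 2.0% | 0.0477 | 0.0523 |
| 0.05 | 0.975 | 5.3% | 0.0443 | 0.0561 |
| 0.10 | 0.949 | 11.1% | 0.0388 | 0.0630 |

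For R² of 0.02 to 0.05 the standard error narrows by 1 − 0.990 = 1.0% to 1 − 0.975 = 2.5%. A chance imbalance in Gd status between arms could also shift the estimate. The documents give nothing from which to size that shift.

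**The case against.** The best defence is that the documents rank themselves. Protocol 8.2 presents its analyses as an outline and leaves the full detail to the SAP. Protocol section 8 says that the double-blind SAP was final before the database was locked and unblinded. The SAS code for secondary models came in with the May 2015 update, made before lock, and brain volume is not among the analyses that the January 2022 update lists as modified after unblinding. It is reasonable to infer that the three-covariate model predates unblinding and is the operative one. That inference stands as likely but is not proved, because the 2015 text is not among the documents. It also does not explain why the more detailed plan lacks a term that the outline names, or square with the claim of alignment.

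Three further objections stand in full. The confirmatory role is conditional on the primary endpoint and seven earlier secondary steps. The precision gain is small and rests on an assumed R². And the primary CSR is listed as completed in SAP 2.4, so substituting a different main model now, without saying so, would itself be a choice of model after unblinding.

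A reader might also infer that the SAP's remark on pseudoatrophy supports Gd adjustment. It does not: the SAP gives it as the reason for measuring change from Week 24, which is how the design already deals with that effect. Nor is there a conflict for the exploratory baseline-to-Week-96 analysis in SAP 4.4.3.5, because the protocol names no covariates for that endpoint.

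**Conclusion.** The inconsistency is confirmed and unexplained, and it should be resolved because the endpoint can act as a gate. Its numerical weight is small: about 1.0-2.5% in the standard error if Gd status explains 2-5% of residual variance, with that range assumed. The two models would mainly disagree near p = 0.05, apart from any shift caused by chance imbalance in Gd status, which the SAP model leaves unadjusted.

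Two stronger readings are tempting. One is that the SAP analysis is biased or inflates type I error. It does neither on this account: with randomised arms, and missing data set aside, leaving a baseline covariate out of a linear model costs precision and does not bias the treatment comparison. The other is that the term was removed after seeing the data, or that the sponsor was free to report whichever model suited. The documents do not show this, and what they say about timing points the other way.

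**What to change.** Add `BGDLESFL` as a main effect to the CLASS and MODEL statements in SAP 4.4.2.10, and to the covariate list in the text, so that the SAP matches protocol 8.2.2.8. Protocol 5.3 lets patients with a contraindication to Gd enrol, so state a rule for them, such as a third level for status not available. State it openly as an addition, because the protocol describes only two levels.

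Because the primary CSR is complete, add a short note saying which model produced the reported brain-volume result, and when and why the Gd term was dropped relative to unblinding. Report the protocol model alongside that result, labelled as such. The reported result should not be silently replaced.

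The cost is one covariate that is already collected and already coded, one additional model run, and a few sentences in the SAP and the final CSR.

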4.4.2.10.1 OLE Phase

This analysis will be extended to include data collected during the OLE period. Percentage change from Week 24, baseline and OLE baseline until the last mature visit will be analyzed.

4.4.2.11 Change in Quality of Life, as Measured by the Short Form 36 Version 2 Physical Component Summary Score from Baseline to Week 96

The Short Form 36 Version 2 (SF-36v2) is a 36-item, self-reported, generic measure of quality of life that has been widely used in multiple disease areas. It is composed of eight health domains: Physical Functioning (PF), Role-Physical (RP), Bodily Pain (BP), General Health (GH), Vitality (VT), Social Functioning (SF), Role-Emotional (RE), and Mental Health (ME). On the basis of these domain scores, the PCS Score and the Mental Component Summary (MCS) Score will be computed. The standard form of the instrument, with a 4-week recall, is being administered in the studies.

Scoring and rules for missing items will follow the SF-36v2 User’s Manual. In brief, scoring for each health domain scale involves (a) recoding item response values, (b) summing recoded response values for all items in a given scale to obtain the scale raw score, and (c) transforming the scale raw score to a 0–100 score. The PCS score is computed by (a) multiplying each health domain Z-score by a scale-specific physical factor score coefficient, (b) summing the resulting products, and (c) converting the product total to a T score. The MCS score is computed in the same manner, using scale-specific mental factor score coefficients.

The PCS scores will be summarized at baseline and Weeks 48 and 96 using descriptive statistics for each treatment group. Data from other unscheduled assessments will not be included in this summary or analysis. The change from baseline to Weeks 48 and 96 in PCS scores will be computed and summarized using descriptive statistics for each treatment group.

For the assessment of differences in the mean change in PCS score during the 96-week comparative treatment period from baseline up to Week 96, MMRM analyses will be undertaken using the same approach as described above in Section 4.4.2.9, except baseline covariates here will be as follows: Baseline PCS score, geographical region (United States vs. ROW), and baseline EDSS score (<4.0 vs. ≥4.0).

Sample SAS code can be found below (SAS code is regarded as “draft” until fully validated at the analysis stage):

```
proc mixed data=PCSS method=REML;  
  class REGION BEDSSCAT ARMCD VISIT USUBJID;
```

```

model change = BPCS REGION BEDSSCAT ARMCD VISIT
BPCS*VISIT ARMCD*VISIT / ddfm= satterthwaite;
repeated VISIT / type=un subject = USUBJID;
lsmeans ARMCD*VISIT / pdiff cl;
ods output lsmeans = lsm; * contains the adjusted means;
ods output difs = dif; * contains treatment differences;
run;

```

